**Table 9-1 Schedule of Assessments**

Study Procedure	Screening Visit	Treatment Period						EoS / ET	F/U
		Cycle 1					Cycle 2-35		
Cycle (C) #	-								
Cycle # and Day		C1D1	C1D2	C1D4	C1D8	C1D11	C1D15	D1	
Window period (days)	-28 to -1	-1*	±1	±3	±3	±3	±3	±3	±7
Informed consent a	X								
Demographics	X								
Eligibility screening	X	X							
Medical history b	X	X							
Physical examination c	X	X			X*		X	X	X
Height, weight d	X d	X					X	X	
Vital signs e	X	X					X	X	
Ophthalmology examination f	X						Q6wk for the first 6 months, then Q9wk thereafter f		X
ECOG g	X						X	X	
12-lead ECG h	X	X		X g				X	
Pregnancy testing i	X							X	
Tumor biopsy j	X								
Hematology and serum chemistry k	X	X			X		X	Every week for Cycles 2 and 3, then D1 of Cycles 4+	X
Coagulation and urinalysis l	X							D1 of each 21-day cycle l	X
Drug administration m		X						D1 of each 21-day cycle	
Pharmacokinetic sample n			See footnote n						
Immunogenicity (ADA) o		X						See footnote o	X
Radiology evaluations (CT or MRI) p	X							Q6wk for the first 3 months, then Q9wk thereafter	X
Concomitant medications		↔							
Adverse events		↔							→

Abbreviations: ADA = anti-drug antibody; D = Day; C = Cycle; CT = computed tomography; ECG = electrocardiogram; ECOG = Eastern Cooperative Oncology Group; EoS = End of Study; ET = Early Termination; F/U = follow-up; MRI = magnetic resonance imaging; Q6wk = every 6 weeks; Q9wk = every 9 weeks

EoS Visit is the safety follow-up visit, conducted  $28\pm 7$  days after the last OBI-999 dose. ET Visit lab assessments will be conducted for patients discontinuing study treatment, if last available tests are before 2 weeks.

\*The - 1 day window (1 day prior) for C1D1 is for safety laboratory assessments. Blood can be drawn 1 day prior to initiation of study drug infusion on C1D1. Safety laboratory results should be available and reviewed by the Investigator prior to the OBI-999 administration.

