#### **14.5 Safety Analysis**

Adverse events will be coded according to Medical Dictionary for Regulatory Activities (MedDRA) version 21.0 or higher and assessed for severity using NCI CTCAE version 5.0. Adverse events will be summarized by system organ class and preferred term and presented in decreasing order of incidence. Dose-limiting toxicities will also be summarized by dose and cohort. The incidence of TEAEs (events with onset dates on or after the start of the study drug) will be included in incidence tables. Events with missing onset dates will be included as treatment-emergent. If a patient experiences more than 1 occurrence of the same AE, the occurrence with the greatest severity and the closest association with the study drug will be used in the summary tables. Serious adverse events and AEs causing discontinuation will be tabulated. All AEs will be listed by patient, along with information regarding onset, duration, relationship and severity to study drug, action taken with study drug, treatment of event, and outcome.

Vital signs, ECG data, ophthalmology, hematology, serum chemistry, coagulation, and urinalysis parameters from baseline and during study will be examined. Treatment-emergent changes in key laboratory parameters will be identified. Clinical laboratory data will be summarized for each time point that specimens are collected. Changes from baseline, for select clinical laboratory analytes may also be explored as specified in the SAP.

Summary tables will be provided for concomitant medications initiated prior to study enrollment or during the study period.

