10.2 DEFINITION OF BASELINE, STUDY VISITS, AND VISIT WINDOWS

Baseline for each assessment is defined as the last non-missing assessment prior to first dose of study drug. If scheduled and unscheduled assessments occurred on the same day and they both can qualify for being baseline, the value from the scheduled assessment should be considered as baseline. The baseline will be presented for each part.

The data will be analyzed according to the visits recorded in the eCRF. No additional visit windows will be applied. In listings, any unscheduled visits will be inserted in the appropriate temporal sequence using visit date and time.

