10.7.1 PRIMARY ENDPOINTS

PART A (DOSE-ESCALATION)

A. AEs/ SAEs and laboratory abnormalities as graded by NCI CTCAE version 5.0*.

Treatment emergent adverse events (TEAEs) are defined as AEs with onset dates on or after the start of study drug until 28 days after the last dose of study drug or if it is present prior to receipt of the study treatment but worsens in severity or increases in frequency on or after the first dose. AEs having both onset and end dates missing will be considered as TEAEs.

TEAEs will be summarized by study part, cohort (by dose level in Part A and by cancer type in Part B), SOC, PT, severity grade, and relationship to treatment. SAEs, deaths, and AEs leading to early treatment discontinuation (collected on Adverse Events eCRF page) will be summarized. The summaries will be sorted by decreasing order of overall incidence of SOCs and decreasing order of overall incidence of PTs within SOCs.

Events reported as “Unrelated” or “Unlikely related” to study drug will be considered as unrelated to the study drug. Events reported as “Possibly related”, “Probably related”, “Definitely related” to study drug or without relationship information will be considered as related to the respective treatment.

Overview summaries of the number and percentages of patients and number of events within the following categories will be provided by study part and by cohort (by dose level in Part A and by cancer type in Part B):

- Any TEAE
- Any TEAE grade ≥ 3
- Any TEAE related to OBI-999
- Any Serious TEAE
- Any Non-Serious TEAE
- Any Serious TEAE related to OBI-999
- Any TEAE leading to death
- Any TEAE leading to discontinuation of OBI-999 (defined as AE with an action taken equals to “Drug Withdrawn”)
- Any Serious TEAE leading to discontinuation of OBI-999 (defined as AE with an action taken equals to “Drug Withdrawn”)
- Any TEAE leading to study discontinuation (defined as AE flagged as Grade 4 infusion reactions and OBI-999 related toxicity, or intercurrent illness in the “End of Study” eCRF

page)

- Any Serious TEAE leading to study discontinuation (defined as AE flagged as Grade 4 infusion reactions and OBI-999 related toxicity, or intercurrent illness in the “End of Study” eCRF page)

Tables by SOC and PT will be displayed for following AEs. Only those AEs marked with * will be analyzed in the aCSR as per sponsor decision.

- TEAEs*
- TEAEs grade ≥ 3 *
- TEAEs related to OBI-999*
- Serious TEAEs*
- Non-Serious TEAEs

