- Serious TEAEs related to OBI-999*
- TEAEs leading to death*
- TEAEs leading to discontinuation of OBI-999*
- Serious TEAEs leading to discontinuation of OBI-999*
- TEAEs leading to study discontinuation*
- Serious TEAEs leading to study discontinuation*

Tables by SOC and PT will display the incidence of events (number of events, number and percentage of patients with any event, number of events of each specific SOC, number and percentage of patients with any event of each specific SOC, number of events of each specific PT and number and percentage of patients with any event of each specific PT).

Tables of TEAEs and serious TEAEs by SOC, PT and worst CTCAE grade (per summarization level) will be presented and will display number and percentage of patients with any event of each specific SOC/PT/CTCAE grade. Number of events will not be displayed. If a patient has multiple AEs with the same SOC or SOC and PT respectively and one of them has missing severity, the highest severity will be used. If the severity is missing for all AEs with the same SOC or SOC and PT, a “missing” category will be added in the summary table.

The following listings will be prepared for AEs. Only those AEs marked with * will be listed in the aCSR as per sponsor decision.

- Pre-treatment AEs
- All TEAEs*
- All TESAEs*
- All TEAEs related to OBI-999*
- TEAEs leading to death (with Grade 5 or “Fatal” as an outcome)*
- All TEAEs leading to discontinuation of OBI-999*
- All TEAEs leading to study discontinuation
- Post-treatment AEs

Number and percentage of patients with laboratory abnormalities with grade ≥ 3 will be provided by study part, by cohort (by dose level in Part A and by cancer type in Part B) and by visit.

B. Dose-limiting toxicities (DLTs) with OBI-999*

A DLT is defined as the occurrence of any of the following events, within the first cycle of treatment that is considered to be at least possibly related to OBI-999:

- Grade 4 neutropenia lasting more than 7 days.
- Febrile neutropenia.
- Grade 4 thrombocytopenia.
- Grade 3 thrombocytopenia with \geq Grade 2 bleeding requiring platelet transfusions.
- \geq Grade 3 fatigue, nausea and vomiting or diarrhea for more than 72 hours despite optimal supportive care.
- Any Grade 4 gastrointestinal toxicity.

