10.8.2 LABORATORY DATA

Baseline results, worst post baseline values (minimum or maximum value as determined by the specific analyte), change from baseline to worst post baseline values for hematology and serum chemistry collected by local laboratories, will be summarized using descriptive statistics, by study part, cohort and overall, in the safety population. Hematology will include Hemoglobin, Hematocrit,

, Platelet count, and White blood cell count with differential. Serum chemistry will include Albumin, Alanine aminotransferase, Alkaline phosphatase, Aspartate aminotransferase, Blood urea nitrogen or Urea, Bicarbonate, Creatinine, Creatine kinase, Electrolytes (Na, K, Cl, Ca, P, Mg), Glucose, Lactate dehydrogenase, Total bilirubin, Total protein, and Uric acid.

Results of coagulation tests (prothrombin time, international normalized ratio, activated partial thromboplastin time), urine analysis data will be summarized at each scheduled visit. Actual laboratory values, and changes from baseline in laboratory values, will be summarized in SI units using descriptive statistics, by study part, dose group, cohort and overall, in the safety population.

For coagulation tests, descriptive statistics will include CV%, geometric mean and geometric SD, calculated as: geometric SD = $\exp(\text{SQRT}(v))$ where v is the squared standard deviation of the log-transformed values.

Shift tables classified by CTCAE grades (grade 0, grade 1, grade 2, grade 3, grade 4, grade 5) from baseline to worst post-baseline grade per cohort, may be presented by selected laboratory tests, where applicable. For laboratory tests for which grades of severity are not defined by CTCAE, results will be graded by the low/normal/high classifications based on laboratory normal ranges.

Urinalysis and microscopic analysis of the urine will be presented in a listing.

For laboratory results reported with a prefix, i.e., "<", "<=", "=>" or ">", the value derived from reported results without a prefix will be analyzed.

Change from baseline scatter plot for selected laboratory analytes will be provided.

Data listings will be produced for all collected laboratory data, including pregnancy test results.

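### Grade 3 or higher laboratory abnormalities are counted only visit by visit, so the plan has no complete per-patient count of severe treatment-emergent abnormalities

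*SAP*

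**What the plan says.** The endpoint "AEs/ SAEs and laboratory abnormalities as graded by NCI CTCAE version 5.0" is primary in Part A and secondary in Part B. SAP 8 and 10.7 star it for the abbreviated report. The laboratory half of SAP 10.7.1 is one sentence: patients with Grade 3 or higher results are counted, and the counts "will be provided by study part, by cohort (by dose level in Part A and by cancer type in Part B) and by visit". For Part B, SAP 10.7.2 refers back to the same analysis.

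Other provisions bear on this table:

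- **Denominator.** SAP 10.1 makes non-missing observations the default.
- **Visits.** SAP 10.2 uses visits as recorded in the eCRF, without windows. On unscheduled visits it says only: "In listings, any unscheduled visits will be inserted in the appropriate temporal sequence using visit date and time". Protocol 9.2 gives them an eCRF page.
- **Schedule.** Protocol Table 9-1 has hematology and chemistry on Days 8 and 15 of Cycle 1, then "Every week for Cycles 2 and 3, then D1 of Cycles 4" onward, plus the end-of-study or early-termination visit.
- **Worst values.** SAP 10.8.2 summarizes "Baseline results, worst post baseline values (minimum or maximum value as determined by the specific analyte), change from baseline to worst post baseline values" on the measurement scale. Shift tables by grade, "from baseline to worst post-baseline grade per cohort, may be presented by selected laboratory tests, where applicable", are optional.
- **Scope of the abbreviated report.** SAP 11 reduces section 10.8.2 to listings, with local results shown as recorded and not normalized. It lists no change to the laboratory count in 10.7.1.
- **Protocol commitment.** Protocol 14.5 states: "Treatment-emergent changes in key laboratory parameters will be identified".

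**The concern.** The safety question is how many patients developed a severe laboratory abnormality on treatment. A table with one row per visit answers a different question: of the patients sampled at this visit, how many were at Grade 3 or higher? The reader cannot get from one to the other, because the rows do not show whether the same patient or different patients are counted. Nor do they show whether the abnormality was there before the first dose.

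This matters here because protocol 4.4 names myelosuppression as an anticipated toxicity. A graded laboratory count does not depend on an investigator's judgment of clinical significance. Once SAP 11 removes the shift tables and worst-value summaries, the by-visit count is the only graded laboratory summary left.

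The SAP uses fuller layouts elsewhere. QTcF and vital-sign categories have a row over all visits (10.8.4, 10.8.3). The ECG and ECOG shift tables take the worst post-baseline observation and expressly include unscheduled visits (10.8.4, 10.8.5). The TEAE tables use the worst grade per patient (10.7.1). SAP 11 withdraws the QTcF, vital-sign, ECG and ECOG summaries from the abbreviated report, so they show what the authors could have specified, not what will be produced.

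**Working it through.** The documents give no figure for laboratory abnormality incidence, so there is nothing to reproduce. The check asks how far a visit row can lie from the per-patient incidence, and in which direction.

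**Number of visits (protocol Table 9-1).** A patient treated for three cycles has 2 post-baseline draws in Cycle 1, 3 + 3 in Cycles 2 and 3, and 1 at end of study: 2 + 6 + 1 = 9. After one cycle the number is 2 + 1 = 3.

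**Assumptions (not in the documents).** The chance p of a Grade 3 or higher value is the same at each visit, taken as 5% to 20%. The correlation ρ between successive visits runs from 0 (brief, scattered) to 1 (fully persistent). No patient drops out.

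**Formula.** After a normal visit the chance of onset is p(1 − ρ), so over K visits

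ever-rate = 1 − (1 − p) × (1 − p(1 − ρ))^(K − 1).

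For p = 5%, ρ = 0, K = 9: 1 − 0.95^9 = 37.0%, and 37.0 / 5 = 7.4.

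Ever-rate divided by per-visit rate, K = 9:

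| p | ρ = 0 | 0.5 | 0.8 | 0.95 | 1 |
|---|---|---|---|---|---|
| 5% | 7.4 | 4.5 | 2.5 | 1.4 | 1.0 |
| 10% | 6.1 | 4.0 | 2.3 | 1.35 | 1.0 |
| 20% | 4.3 | 3.3 | 2.1 | 1.3 | 1.0 |

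With K = 3 and ρ = 0 the ratio is 2.9, 2.7 and 2.4 for p = 5%, 10% and 20%.

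**Direction, in a stage 1 cohort of 9 (size from protocol 14.1; patterns invented for illustration).**

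| Pattern | Visit row | Per patient |
|---|---|---|
| 3 patients, once each, at different visits | 1/9 = 11% | 3/9 = 33% |
| 3 patients, all at the same visit | 3/9 = 33% | 3/9 = 33% |
| 1 patient, at a visit where only 2 are still sampled | 1/2 = 50% | 1/9 = 11% |
| 2 patients severe at baseline and throughout, none new | 2/9 = 22% at every visit | 0% treatment-emergent |

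The first pattern reads low by a factor of 3, the second agrees, and the last two read high.

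**Other summaries.** Reading the sections together, the grade shift table in 10.8.2 was optional and is now dropped. The worst-value summary there was never by grade and is also dropped. The AE tables do use worst grade per patient, but under protocol 12.4 and 12.5.1 a laboratory result becomes an AE only if the investigator considers it clinically significant.

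**The case against.** Several points on the other side have force.

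- **By-visit layout follows the protocol.** Protocol 14.5 also calls for laboratory summaries at each collection time, and its sentence on treatment-emergent changes prescribes no particular table. This stands: the by-visit table is not itself a departure. But it cannot identify treatment-emergent changes, and no other planned summary does so completely.
- **AE and DLT tables cover severe cytopenia.** Results needing intervention are AEs, and Table 8-1 links Grade 2 to 4 toxicity to dosing action, so many Grade 3 or higher cytopenias will probably be reported. They would enter the starred Grade 3 or higher TEAE table. DLTs cover some Cycle 1 cytopenias in Part A. This is a substantial but partial substitute, since it depends on investigator judgment.
- **Baseline matters less for the key analytes.** Inclusion criterion 7 limits entry values of neutrophils, platelets, hemoglobin, ALT, AST and bilirubin. The missing comparison therefore bears mainly on graded analytes without an entry limit.
- **Small, stopped study with full listings.** This limits the consequences. The listings let a reader rebuild the count, but only by hand and with individually chosen rules.

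A reader might infer that unscheduled values are excluded from the table, so that mid-cycle low points after Cycle 3 appear nowhere. The documents do not say that. SAP 10.2 orders unscheduled visits within listings, analyzes visits as recorded in the eCRF, and bars nothing from tables. Their handling is unspecified, and the table shells are in a separate document. Sparse sampling from Cycle 4 is a schedule question: no table recovers values that were never drawn.

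**Conclusion.** The point holds as a gap in how the table counts. As written, SAP 10.7.1 cannot give the per-patient incidence of treatment-emergent Grade 3 or higher laboratory abnormalities, and no other summary kept for the abbreviated report gives it completely.

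A reader might go further and conclude that the table reads several-fold low. The documents do not support that. They give neither a per-visit rate nor a measure of persistence. Over nine visits the ratio runs from 1.0 to 7.4 under the assumed rates of 5% to 20%, and is close to 1 when abnormalities persist. Baseline values and shrinking denominators push the other way. What can be said is that the discrepancy has unknown size and direction, so a reader cannot correct for it.

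SAP 10.7.1 and SAP 11 also need reconciling. If the listing-only statement for 10.8.2 also governs the 10.7.1 count, the starred endpoint has no graded laboratory summary at all. If it does not, the by-visit table is the only one. Either reading calls for a correction.

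**What to change.** Add to SAP 10.7.1:

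> For each graded analyte and direction, the number and percentage of patients whose worst post-baseline grade (scheduled and unscheduled values, from first dose to 28 days after last dose) is 3 or higher and exceeds the baseline grade will be given by study part and cohort. The denominator is patients with at least one post-baseline value of that analyte.

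Baseline is already defined in SAP 10.2, and the 28-day limit matches the TEAE definition. Because Table 9-1 allows ±7 days around the end-of-study visit, state whether a sample drawn late within that window counts.

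Keep the by-visit counts as supportive. In SAP 11, state that the 10.7.1 laboratory summaries are retained although 10.8.2 is reduced to listings, and that grades are assigned against the local reference ranges, since local results are not normalized. A separate shift table for selected analytes is not needed.

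The cost is SAP wording and one additional summary from results already collected. The by-visit table already requires each result to be graded. The new steps are the worst grade per patient and its comparison with baseline.

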- Any \geq Grade 3 non-hematological toxicity (except Grade 3 fatigue, nausea, vomiting, or diarrhea lasting $<$ 24 hours with optimal therapy, Grade 3 non-hematologic laboratory abnormalities that resolve to Grade 1 or baseline within 14 days).

All TEAEs, unless they are determined to be not related to study drug will be taken into consideration in determining DLTs. The period for DLT observation is 21 days from the start of first dose of OBI-999 (i.e., Day 1).

DLTs (not to be programmatically derived; will be analyzed as collected on eCRF) will be displayed by dose level in a frequency table in decreasing order of incidence. AEs will be graded according to the NCI CTCAE V5.0. All TEAEs unless they have been determined to be not related to study drug will be DLTs and will be summarized by dose, SOC and PT. A listing of DLTs will be prepared.

C. MTD and RP2D of OBI-999

At the time of this version of the SAP, Part A (Dose-Escalation) was completed. The RP2D of 1.2 mg/kg was identified during SRC review.

PART B (COHORT-EXPANSION)

A. Objective Response*

Overall tumor response (not to be programmatically derived; will be analyzed as collected on eCRF) will be listed by cancer type and visit. For each patient, best overall response (BOR) is defined as the best overall tumor response (complete response [CR], partial response [PR], stable disease [SD], and progressive disease [PD], or not evaluable [NE]) from the start of treatment until disease progression, recurrence or end of study. In general, the patient's best response assignment will depend on both the tumor measurement and confirmation criteria.

If an NE response is determined at a time point, this response will be ignored and subsequent non-NE responses will be used for the confirmation. For example, the sequence of tumor assessments: PR, NE, NE, CR, SD, that had more than two consecutive NEs, the third subsequent non-NE response (CR) is used as the confirmation of the first PR for best overall response derivation.

A requirement for SD is that it should be met at least once \geq 6 weeks after the first dose of trial treatment, otherwise the best response will be NE.

The criteria for confirmation of the response are summarized in the following table (Eisenhauer

et al, 2009):

Overall response first time point	Overall response subsequent time point	Best overall response
CR	CR	CR
CR	PR	SD, PD or PR [1]
CR	SD	SD provided minimum criteria for SD duration met, otherwise PD

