11. DEVIATIONS FROM ANALYSIS AS DESCRIBED IN THE PROTOCOL

In the section §14.2 of the protocol the safety population is defined as all enrolled patients who receive at least 1 dose of study drug. The population used for analysis of clinical activity is defined as all enrolled patients who received at least one dose of study drug and had at least one follow-up tumor assessment scan, but it was not clearly stated this is the efficacy population. We clearly defined it in section §8 of the SAP.

The DOR is defined in section 14.3 of the protocol as the time from date of confirmed PR or CR to date of progression, but as we are applying a censoring rule to patients who are alive at the time of the analysis, we updated the definition in section 9.7.1 of the SAP to time from date of confirmed PR or CR to date of progression or death (from any cause).

OBI-999 2.0 mg/kg was planned to be administered in Part A but this dose was not administered to any subjects in Part A due to the toxicity observed with the 1.6 mg/kg dose. For this reason, this cohort will not be presented.

Efficacy endpoints will be analyzed in the safety and efficacy populations, because the definition of the efficacy population specifies that patients must have at least one follow-up assessment scan and so is closer to a per protocol population.

DLTs will not be derived and will be presented as collected on the eCRF. The following DLTs have been updated:

- “≥ Grade 3 fatigue, nausea and vomiting or diarrhea that does not resolve to Grade 1 or Baseline within 72 hours despite optimal supportive care” has been revised to “≥ Grade 3 fatigue, nausea and vomiting or diarrhea for more than 72 hours despite optimal supportive care”.
- “Any other Grade 3 or Grade 4 non-hematological toxicity (except Grade 3 fatigue, nausea, vomiting, or diarrhea lasting < 24 hours with optimal therapy, Grade 3 non-hematologic laboratory abnormalities that resolve to Grade 1 or baseline within 14 days)” has been

revised to. Any \geq Grade 3 non-hematological toxicity (except Grade 3 fatigue, nausea, vomiting, or diarrhea lasting < 24 hours with optimal therapy, Grade 3 non-hematologic laboratory abnormalities that resolve to Grade 1 or baseline within 14 days)".

On 10 November 2023, Sponsor stated they stop the OBI-999-001 study and elected to generate an aCSR. Therefore, as per sponsor decision, the planned analyses have been changed to:

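### SAP 10.7.1 says every Part A TEAE not judged unrelated is a DLT, contradicting its own definition of listed first-cycle events recorded on the eCRF

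*SAP*

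**What the plan says.** SAP 10.7.1, Part A, item B opens with the definition: "A DLT is defined as the occurrence of any of the following events, within the first cycle of treatment". The event must also be at least possibly related to OBI-999. Seven kinds of event follow. Six carry an explicit Grade 3 or Grade 4 threshold; the seventh is febrile neutropenia.

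Three statements then set out how that definition is applied:

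- On candidates: "All TEAEs, unless they are determined to be not related to study drug will be taken into consideration in determining DLTs".
- On timing: "The period for DLT observation is 21 days from the start of first dose of OBI-999".
- On data source: "DLTs (not to be programmatically derived; will be analyzed as collected on eCRF) will be displayed by dose level". SAP 11 repeats this: "DLTs will not be derived and will be presented as collected on the eCRF".

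In the same paragraph as the data-source rule comes the sentence at issue: "All TEAEs unless they have been determined to be not related to study drug will be DLTs and will be summarized". It specifies a summary by dose, SOC and PT. A DLT listing is also required.

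Two rules in item A of the same section fix what that sentence would cover. TEAEs include "AEs with onset dates on or after the start of study drug until 28 days after the last dose of study drug", at any grade. Possibly, probably and definitely related events count as related, and so do events "or without relationship information will be considered as related to the respective treatment".

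**The concern.** One subsection gives two incompatible answers to which events are DLTs. The definition makes related TEAEs candidates to be judged against a list. The later sentence makes them DLTs outright.

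The sentence is hard to set aside as harmless, because it is the only place that specifies a DLT summary by SOC and PT. Item A lists 11 SOC/PT tables and none is for DLTs. Protocol 14.5 asks only for a summary by dose and cohort. Protocol 6.2 has the narrower candidate wording, but Protocol 14 says the SAP prevails where the two differ, so the protocol cannot be relied on to correct it.

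At stake is the accuracy of a primary-endpoint output. SAP 8.1 lists DLTs as a Part A primary endpoint and stars them for the abbreviated report. A table built on the sentence would overstate DLTs and disagree with the eCRF-based DLT listing. It could also seem to conflict with the 3+3 rule in SAP 5.1.1, under which a dose is the MTD only if at most 1 of 6 patients has a DLT. That would happen if two or more of six patients at a tolerated dose had any related TEAE.

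**Working it through.** The plan gives no figure to reproduce. The check compares the two rules, followed by arithmetic on the windows.

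**The two rules compared**

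| Feature | Definition and eCRF rule (10.7.1 B; SAP 11) | The sentence at issue, read with the TEAE rules in 10.7.1 A |
|---|---|---|
| Event type | Seven listed kinds | Any |
| Grade | Thresholds as listed | Any |
| Timing | First cycle, 21 days | First dose to 28 days after last dose |
| Relationship | At least possibly related | Not determined to be unrelated, so missing relationship counts |
| Source | DLTs as collected on the eCRF | TEAE status and relationship |

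Two examples show that the rules select different events:

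- Related Grade 2 nausea in Cycle 1 falls inside the window but below the listed grade. It is not a DLT by the definition but is one by the sentence.
- A related Grade 1 event at the start of Cycle 5 (Day 4 × 21 + 1 = 85) fails the list, the grade threshold and the window. It is still a DLT by the sentence.

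The set the sentence selects is close to that of the starred related-TEAE table restricted to Part A. SAP 10.7.1 A groups unrelated and unlikely events as unrelated, and everything else as related.

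**Was a redefinition intended?** SAP 11 itemises two changed DLT criteria and restates the eCRF rule. It does not list a change making all related TEAEs DLTs. Together with the candidate wording in Protocol 6.2, this points to a slip.

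**Windows**

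Inputs: DLT window of 21 days from first dose (10.7.1 B); TEAE window to 28 days after last dose (10.7.1 A); 21-day cycles, at most 35 (SAP 5.1.1). Day 1 is the first dose, so the DLT window is taken to end on Day 21.

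- TEAE window end = day of last dose + 28.
- One dose: 1 + 28 = Day 29, which is 29 − 21 = 8 days past the DLT window.
- 35 cycles with no skipped dose: last dose on Day 34 × 21 + 1 = 715; 715 + 28 = Day 743, which is 743 − 21 = 722 days past it.

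If the 21 days are counted as ending on Day 22, each excess falls by one day (7 and 721). On either count the nominal TEAE window is the longer one, even after a single dose.

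**Over-count.** The documents give no number of DLTs or related TEAEs by dose, so the excess in events or patients cannot be calculated.

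**The case against.** The strongest reply is that the right rule is explicit and repeated. The eCRF instruction is in the same paragraph as the sentence and again in SAP 11, and the definition and window come just before it. A programmer would have to derive DLTs from relationship data, which that paragraph forbids. SAP 11 shows that nobody meant to redefine the endpoint. Part A enrolled 22 patients, so a DLT table full of low-grade events would stand out against the DLT listing and the related-TEAE outputs. No decision depends on it: the Safety Review Committee had already determined DLTs and selected 1.2 mg/kg, and the study has been stopped with only an abbreviated report to follow.

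Much of this stands. It is a drafting contradiction, dose selection is untouched, and other outputs would help expose the error. Two further points are also fair. The frequency table by dose level and the summary by SOC and PT may be one table, so a clash between two tables is conditional. The day counts describe nominal windows and do not measure impact: Day 743 needs all 35 cycles, and a patient who died or left early would add no extra follow-up.

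The reply does not remove the contradiction. Even with a single table, the required eCRF-based listing would disagree with one built on the sentence. The table shells are in a separate document (SAP 13) that was not available, so it cannot be confirmed that the sentence was disregarded.

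**Conclusion.** The concern holds. SAP 10.7.1 states a rule for a starred primary-endpoint output that is incompatible with its own definition, window and data source, and that would give a wrong table if followed. The conclusion rests on the text alone. The window comparison assumes that Day 1 is the first dose and, for Day 743, that no dose is skipped.

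The effect is confined to reporting. It reaches the DLT summary by SOC and PT, and only if the sentence is programmed as written. Its numerical size is unknown. The sentence should be corrected, but it does not call the RP2D into question.

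**What to change.** Replace the sentence with: *Only events recorded as DLTs on the eCRF will be summarized by dose level, SOC and PT.* This keeps the planned summary and agrees with the definition, the 21-day window and SAP 11.

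If the table has already been programmed or produced, check it against the DLT listing and confirm that the table shell uses the eCRF DLT record.

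The cost is one SAP sentence and, where a table exists, that check. No new data and no new output are needed.
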